3. **Children who do not have STEC infection will avoid unnecessary blood tests, intravenous fluids and repeat visits:** As ~10% of eligible children will have STEC infection,^{25,26} the routine performance of blood tests, administration of intravascular hydration, and frequent monitoring is unnecessary in the vast majority of children with hematochezia. As such, knowledge that a result will be rapidly available will enable clinicians to confidently discharge children without performing unnecessary procedures. Those who test positive can be recalled to the ED for the appropriate management.
4. **Children will have alternative etiologies identified rapidly:** The BioFire FilmArray will also enable the rapid identification of other pathogens, some of which will require immediate therapy such as *Shigella sp.*, *Clostridium difficile*, and others that have public health implications such as *Salmonella sp.*, and norovirus.
5. **Children who do not have infectious gastroenteritis will be rapidly identified:** Children with a negative BioFire FilmArray will also be identified. This would raise the suspicion for alternative etiologies.
6. **Transmission will be reduced:** The rapid identification of infected children has the potential to reduce spread, which is common and occurs early in the course of disease. Transmission might be reduced by separating infected index cases from their at risk siblings.²⁷

3 Study Objectives

The rapid identification of STEC-infected children will enable the provision of appropriate and timely care to such children. The rapid identification of other enteric pathogens (bacteria, virus, parasite) will enable the provision of targeted therapies as appropriate and the withholding of avoidable interventions. It will also provide information for clinicians to consider alternate, non-infectious etiologies as appropriate. We hypothesize that the **BioFire FilmArray can be used selectively in children with hematochezia to identify children with STEC infection and therefore will expeditiously identify children in need of therapeutic interventions and those for whom blood testing, intravenous fluids, and follow-up visits are unnecessary.**

Knowledge of the etiology early in the course of disease will enhance the provision of a patient-level precision medicine approach to what is otherwise an ill-defined symptom.

Research Questions

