Biofire FilmArray™: The Health Canada and Food and Drug Administration-approved, multiplex Biofire FilmArray™ Gastrointestinal Panel can detect 22 analytes: *Campylobacter (C. jejuni, C. coli, and C. upsaliensis)*, *Salmonella*, *Shigella/Enteroinvasive E. coli (EIEC)*, *Vibrio (V. parahaemolyticus, V. vulnificus, and V. cholerae)*, *Yersinia enterocolitica*, Shiga-like toxin-producing *E. coli* (STEC) *stx1/stx2*, Enterotoxigenic *E. coli* (*ETEC*) *lt/st*, *E. coli O157*, *Clostridium difficile* (Toxin A/B), *Plesiomonas shigelloides*, Enteroaggregative *E. coli* (*EAEC*), Enteropathogenic *E. coli* (*EPEC*), norovirus GI/GII, rotavirus A, adenovirus F40/41, astrovirus, sapovirus (I, II, IV and V), *Cryptosporidium*, *Entamoeba histolytica*, *Giardia lamblia*, and *Cyclospora cayetanensis*. A single instrument can test one stool sample in approximately 1 hour with 2 minutes of hands-on time. After adding 200 µL of stool specimen in Cary Blair and hydration solution to the FilmArray pouch, the system performs nucleic acid extraction, nested multiplex polymerase chain reaction and lastly, endpoint melting curve analysis with the

Ethics ID: REB17-1916

Title: Improvements Through the Use of a Rapid Multiplex PCR Enteric Pathogen Detection Kit in Children with Hematochezia

PI: [name]

Version 5.0 – May 16, 2018

Previous REB Approved Version Date: January 12, 2018

Page 9 of 19

FilmArray software. For this study, the BioFire FilmArray will be run as a research test at CLS and it will not go through full verification and implementation procedures at CLS. The product insert recommendations will be followed for verification purposes.

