Rectal Swabs: The APPETITE team has been evaluating the use of rectal swabs for over two years now and we have demonstrated that rectal swabs are a suitable alternative specimen when stool is unavailable.²⁸ In brief, we insert a sterile flocked rectal swab (FLOQSwab, Copan Italia, Brescia, Italy) into the rectum. It is then rotated a full circle once and then transported in modified Cary-Blair media. The current APPETITE protocol employs the Luminex xTAG Gastrointestinal Panel Platform and requires a full day for extraction (hence the switch to the Biofire FilmArray for the current study proposal). When compared with paired stool samples on 1142 children, overall agreement is 90% (95% CI: 88, 92) with positive test result agreement of 98% (95% CI: 96, 99). As it relates to bacterial pathogens the overall agreement is 93% (95% CI: 92, 95) with positive bacteria test result agreement of 81% (95% CI: 74, 86). These results were achieved through the use of a specimen procurement approach that would be replicated in the current proposal.

In a 3-centre project currently underway in the U.S. employing rectal swab analysis on the Biofire FilmArray platform they have found performance of the rectal swab to be comparable to stool for detection of pathogens.²⁹ Importantly, there were no discrepancies for bacterial or STEC targets. They concluded that rectal swab collection at the time of the patient visit enables rapid testing and the generation of actionable results in the acute care setting when a stool specimen cannot be provided.

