4.4.2 Statistical Methods

All analyses will be undertaken by the intention-to-treat (ITT) principle. Patients who drop out or crossover will be followed and included in the ITT analysis. All statistical tests will be two-sided. Baseline characteristics will be analyzed and compared. Sensitivity analyses will be performed to assess the possibility and consequences of non-random loss to follow-up. The proportion of children who have any blood testing performed within 72 hours of randomization, **the primary outcome**, will be analyzed by comparing proportions utilizing a Fisher’s Exact test. We will use an alpha level of 0.05 for statistical testing.

The overall significance level for statistical tests on the **secondary outcomes** will be set at 0.05 with adjustment for multiple comparisons performed using a Bonferroni correction.

Ethics ID: REB17-1916

Title: Improvements Through the Use of a Rapid Multiplex PCR Enteric Pathogen Detection Kit in Children with Hematochezia

PI: [name]

Version 5.0 – May 16, 2018

Previous REB Approved Version Date: January 12, 2018

Dichotomous outcomes to be evaluated include 1) intravenous rehydration, 2) ED revisits, 3) any healthcare revisits and 4) hospitalization within the subsequent 14 days. Clinical outcomes will also include development of 5) HUS, 6) Kidney Disease Improving Global Outcomes Stage 2 or 3 creatinine based acute kidney injury,³¹ 7) antibiotic use, and 8) diagnostic imaging.

Recursive partitioning analysis will be employed to identify clinical features that select candidates for BioFire testing that maximize specificity and sensitivity to identify STEC patients. Analyses will be performed blinded to allocation assignment.

5 Adverse Event Reporting

Anticipated disease outcomes (listed below) are sought to be a natural continuation of the disease and as a result, the following will not be reported to REB:

1. IV insertion
2. Blood tests
3. Abdominal pain
4. Fever
5. Vomiting
6. Diarrhea
7. Bloody stool
8. Dialysis
9. Renal abnormalities
10. Hematological abnormalities
11. Biochemical abnormalities
12. Transfusions
13. Seizures
14. Hospital admissions
15. Other known complications of STEC infection

6 Data Handling and Record Keeping

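### Section 5 exempts dialysis, renal abnormalities, seizures and admissions from ethics-board reporting in every child, although a falsely negative BioFire result could contribute to them

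*Combined protocol and SAP*

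**What the plan says.** Section 5 (Adverse Event Reporting) is one sentence and a list. The rule is that "as a result, the following will not be reported to REB". The reason given for it is that the listed events are regarded as the disease running its course. The 15 items include dialysis (item 8), "Renal abnormalities" (9), hematological abnormalities (10), seizures (13), "Hospital admissions" (14) and "Other known complications of STEC infection" (15). The last item can be read to cover HUS and death from it. Nothing restricts the list by arm, STEC status, BioFire result, severity or relatedness. The documents name no event that must be reported, no causality assessment and no safety board.

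The intended effect on care is stated elsewhere. Section 2 expects that "knowledge that a result will be rapidly available will enable clinicians to confidently discharge children without performing unnecessary procedures", with children who test positive called back. Section 4.1 leaves treatment to the ED physician who receives the result. It also says of the test that "it will not go through full verification and implementation procedures at CLS", and adds that the product insert will be followed for verification.

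**The concern.** The stated reason for the exemption is that the events belong to the disease and not to the study. That does not fit a trial whose intervention works by changing how closely children are tested, hydrated and observed. The list even includes IV insertion and blood tests. Any blood test is the primary outcome and IV fluid use is a secondary one, so the plan itself expects the intervention to change both.

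If a child with STEC has a negative, failed or undelivered result and is sent home without blood tests, a later dialysis, seizure or admission is a possible consequence of the study procedure. Under the rule as written, that event would not go to the ethics board, and the documents describe no other body that would look at the single case. Section 8 speaks of moving the test into standard care if it proves safe and effective. A judgement of safety from 60 children would rest largely on such single cases.

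**Working it through.** **Children covered.** Section 4.4.1 gives 54 children, raised to 60. This reproduces: the exact two-sided Fisher test at 60% versus 20% has 80.2% power with 27 per arm (79.9% with 26), and 54 / (1 − 0.10) = 60. The allocation ratio is not stated; the budget's 30 tests suggest 30 per arm, which I assume.

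**Other inputs.**
- STEC among eligible children: about 10% (Section 2).
- HUS given infection: about 15% (Section 1). This is an E. coli O157 figure, applied here to all STEC as an assumption.
- BioFire sensitivity for STEC: not given, so a range is used. The 81% (95% CI 74 to 86) in Section 4.1 is agreement of rectal swab with stool for all bacteria on the Luminex platform. It serves only as a pessimistic anchor.

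**Background counts.** Expected STEC in the BioFire arm: 30 × 0.10 = 3. Children without STEC who still fall under the exemption: 60 × 0.90 = 54. Expected HUS: 30 × 0.10 × 0.15 = 0.45 per arm, or 0.9 in the trial.

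**Missed cases.** With sensitivity Se:
- P(at least one missed STEC child) = 1 − [1 − 0.10 × (1 − Se)]^30
- P(at least one missed STEC child who develops HUS) = 1 − [1 − 0.10 × (1 − Se) × 0.15]^30

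| Se | at least one missed | at least one missed with HUS |
|---|---|---|
| 74% | 55% | 11% |
| 81% | 44% | 8% |
| 86% | 34% | 6% |
| 95% | 14% | 2% |
| 99% | 3% | 0.4% |

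For example, at 81%: 0.10 × 0.19 × 0.15 = 0.00285, and 1 − 0.99715^30 = 0.082. At 100% sensitivity both columns are zero. The right-hand column is the relevant one, because it counts a listed harm and not just a missed infection. It does not require that the result changed the child's care.

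**What the other sections still capture.**
- Section 4.1.1 collects HUS, acute kidney injury, renal replacement therapy, and hospital and ICU admission by chart review. Seizures and death are not listed outcomes.
- Section 4.4.2 names HUS, kidney injury and hospitalization for analysis, but not renal replacement therapy or ICU admission.
- Kidney injury is creatinine-based in Section 4.4.2, so fewer blood tests in the BioFire arm would also mean less chance of detecting it there.
- The Day 14 contact asks about visits, admissions and procedures. The Day 28 record review is worded as optional (Sections 4.1 and 4.3).
- Culture continues in the BioFire arm. In the 2014 outbreak a positive culture came at a median of 120 hours (5 days) after first presentation. Section 2 expects point-of-care swabs to start processing about 30 hours sooner. HUS appears 5 to 13 days after diarrhea onset. Culture may therefore correct a false negative only shortly before, or within, that window.

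**The case against.** Several points on the other side stand.

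A reader might infer that a false negative would cause these events. The documents do not go that far. Section 1 says that no therapy is proven to prevent HUS or to lessen kidney injury once it is established, and that volume expansion may help. They support no more than a possible contribution.

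A reader might also infer that the safety signal is lost altogether. It is not: most of these events are secondary outcomes, and BioFire-arm specimens go for routine culture with a back-up stool requested. But a chart-review comparison at the end of the trial is not timely review of one case.

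The 44% chance of a missed infection should not be read as the size of the harm. It applies agreement for all bacteria, from another platform, to all 30 children, although swabs are used only when stool is unavailable. Section 4.1 reports no STEC discrepancies for swabs on BioFire itself, and Section 1 describes the device as approved and validated. The true figure may lie near the low end of the table.

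Finally, Section 1 commits the study to Good Clinical Practice and institutional requirements. These may oblige staff to report an unanticipated, test-related event despite the list. The documents do not show whether they do, so it cannot be said that every such event would go unreported. But a specific list is what staff are likely to follow, and this one points the other way.

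**Conclusion.** The point holds as a fault in a stated rule. The exemption rests on the premise that the events are independent of the study, and the trial's own hypothesis contradicts that premise for children in whom STEC is missed. The gap is the absence of prompt, result-linked ethics review; it is not loss of all data and not proof of harm.

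Such a case is unlikely in a trial this small: about 8% at 81% sensitivity, 2% at 95% and 0.4% at 99%. These figures rest on 30 BioFire children, 10% STEC, the O157 risk of HUS applied to all STEC, and a sensitivity that the documents do not supply. The recommendation does not depend on the higher figure: if the case occurs, the rule as written keeps it from the board. The rule should be changed. No sample size or power figure is affected.

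**What to change.** Keep the Section 5 exemption for anticipated events, but except from it HUS, dialysis, seizure, ICU or unplanned admission, and death when they occur:

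(a) in any child whose BioFire STEC result was negative, invalid or not returned and in whom STEC is later found; or

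(b) in either arm, in any child sent home from the enrolment visit without blood tests.

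Report these events to the ethics board and tabulate them by arm, adding seizures and death to the events collected. Both triggers rest on recorded facts, so neither needs a causality assessor. Trigger (b) covers both arms because Section 4.4.1 implies that 40% of controls (12 of 30), as well as 80% of BioFire children (24 of 30), have no blood test within 72 hours; a trigger in one arm only would make reporting differ by arm.

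The cost is a few lines in Section 5 and a small number of reports. About 0.9 HUS cases are expected in the whole trial on the assumptions above. The documents give no rate for unplanned admissions, so that part of the count cannot be fixed in advance. The change alters no treatment decision and no primary analysis.

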6.1 Confidentiality

Data collected on paper will be stored in a locked cabinet in a locked office of a securely accessed building.

Ethics ID: REB17-1916

Title: Improvements Through the Use of a Rapid Multiplex PCR Enteric Pathogen Detection Kit in Children with Hematochezia

PI: [name]

Version 5.0 – May 16, 2018

Previous REB Approved Version Date: January 12, 2018

Page 14 of 19

Data will be entered from paper to REDCap, or entered directly into REDCap, which is a data capture system that has been validated by Health Canada. REDCap access will be determined based on project involvement. Only the investigators and research staff listed on the ethics submission will have access to data. Additionally the data management team will have administrative access to the database and the servers on which it resides. The data management team will only access study data as required to perform maintenance and support duties.

The database contains sensitive patient information as well as personal identifiers however, each patient is assigned a study ID that is used to communicate about the patient. Information from the database will be coded and stored into the secure server. The database will have robust and modern security principles enforced in an auditable fashion as outlined in the Health Information Act and in most cases in line with the guidelines set out in the FDA's CFR Part 11 Guidance document.

Deidentified data may also be stored on secure network drives including Alberta Health Services, University's hydrogen drive and computers on the ProvLab Laboratory Information System. Authorized access will be granted to relevant research team members and requires a specific user ID and password.

Because this study will recruit participants in an ED setting, the likelihood of one study participant speaking with another is very low. These participants will likely only have one visit, at which time they will be enrolled. All follow up will be done confidentially over the phone or by secure email.

6.2 Records Retention

Name of patient is collected and kept for future contact after data collection has been completed only if the patient consents to contact for a future research study.

6.3 Regulatory Binder

A regulatory binder containing all information pertinent to the study will be kept.

7 Budget

PEMRAP	\$2,500 – coordination, training, supplies, data collection
CLS	\$100/test x 30 = \$3,000

Ethics ID: REB17-1916

Title: Improvements Through the Use of a Rapid Multiplex PCR Enteric Pathogen Detection Kit in Children with Hematochezia

PI: [name]

Version 5.0 – May 16, 2018

Previous REB Approved Version Date: January 12, 2018

Page 15 of 19

Flocked Rectal Swabs	\$0.75 x 30 = \$23
Study Coordinator	Start-up: \$40/hr x 37.5 hrs/wk/FTE x 0.5 FTE x 8 weeks x 1.23 (benefits) = \$7,380 Ongoing: \$40/hr x 37.5 hrs/wk/FTE x 0.1 FTE x 52 weeks x 1.23 (benefits) \$9,594
Database/randomization	\$2,500 – database creation, design, logic, limits, and computer based randomization
Statistical Analysis	To be done by [name] (with consultation requested as needed)
Biofire FilmArray	\$29,000 (in-kind for device, training, service, kits)
TOTAL	\$24,997

We have been working with bioMérieux Canada, the distributor of the **Biofire FilmArray** on approaches to integrate rapid diagnostics to improve the care of children with STEC infection. For the current study proposal they have agreed to provide an in-kind device (\$6,000/year), service (\$5,000/year), and 100 test kits (\$18,000) for total in-kind support of \$29,000.

8 Publication Plan

We will interpret our findings in the context of value added. We will compare the outcomes in children randomized to testing with the Biofire FilmArray and those randomized to standard of care. We will evaluate the role the Biofire FilmArray might play in rapidly identifying the etiology of the hematochezia compared with standard testing. We will explore the role the Biofire FilmArray might play in selectively identifying children who require blood tests, intravascular volume expansion and close monitoring.

If this study yields findings of clinical relevance, we would seek subsequent funding to conduct an economic evaluation to determine if the cost of care provided to individuals randomized to testing with the BioFire FilmArray is less than that provided to children in the standard care group. We will employ data collected regarding utilization of testing (BioFire FilmArray, blood, urine, stool), diagnostic imaging, ED care (i.e. visit cost), physician billing, and medication administration to evaluate the relative cost of the two approaches and we will determine the cost per case of STEC infection identified.

Appendix 1: Quantified time lag to diagnosis in Alberta's children.

Ethics ID: REB17-1916

Title: Improvements Through the Use of a Rapid Multiplex PCR Enteric Pathogen Detection Kit in Children with Hematochezia

PI: [name]

Version 5.0 – May 16, 2018

Previous REB Approved Version Date: January 12, 2018

Page 19 of 19
